5.5. ANALYSIS POPULATION

The Screened Population includes all the subjects who are screened for this study and have any data captured in the EDC.

The Full Analysis Set includes all subjects who receive at least one dose of study drug during the trial and who have any follow-up data. The efficacy and safety analysis will be performed based on Full Analysis Set.

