14.3 Analysis Populations

The analysis population includes all patients who receive at least one dose of study drug.

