5. GENERAL STATISTICAL CONSIDERATIONS

Descriptive summaries will be provided where appropriate for each of the primary and secondary variables.

Continuous, quantitative (absolute values at each time point and change from baseline if applicable) variable summaries will include the number of subjects (N) with non-missing values, mean, standard deviation (SD), standard error (SE), median, minimum, and maximum, unless otherwise specified.

Categorical, qualitative, variable summaries will include the frequency and percentage of subjects who are in the particular category. In general, the denominator for the percentage calculation will be based upon the total number of subjects in the study population for the cohorts, unless otherwise specified.

All data collected on eCRF will be presented in listings.

All analysis will be performed using SAS® Software version 9.4 or later.

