5.3. VISIT WINDOW

Enrolled subjects will attend a total of 3 morning trial visits:

- Visit 1 will be considered Week 1, Day 1 (first day/week of dosing)
- Visit 2 will be performed during Week 13 (± 1 week), 5 days (± 1 day) post-dose
 - If during Week 12, Visit 2 must occur on Days 82 to 84
 - If during Week 13, Visit 2 must occur on Days 89 to 91
 - If during Week 14, Visit 2 must occur on Days 96 to 98
- Visit 3 will be performed during Week 26 (± 1 week), 5 days (± 1 day) post-dose
 - If during Week 25, Visit 3 must occur on Days 173 to 175
 - If during Week 26, Visit 3 must occur on Days 180 to 182
 - If during Week 27, Visit 3 must occur on Days 187 to 189

Subjects <3 years old at Visit 1 will have a total of 4 morning trial visits including the above 3 visits and the addition of:

- C_{max} Visit to be performed during Week 4 (+1 week), 1-2 days after the 4th or 5th dose
 - If during Week 4, C_{max} Visit must occur on Days 23-24
 - If during Week 5, C_{max} Visit must occur on Days 30-31

Post-baseline unscheduled visit (occurred after the date of initiation of the first dose) or end of study visit (early termination visit) will be mapped to the post-baseline scheduled visit with the closest target study day for each scheduled assessment according to [Table 2](#). If the unscheduled visit is in the middle of two scheduled visits, map it to the later one. After mapping, if there are more than one visit in the same window, the visit closer to the target assessment day will be used. If more than one visit has the equal distance to the target day then the later one will be used, if more than one visit on the same day, use the time or the sequence number to select the later record. For listings and shift tables, all data points will be included.

Table 2: Analysis Window

Visit	Screening	Visit 1	C _{max} Visit	Visit 2	Visit 3/ET
Week	Weeks -4 to -1	Week 1	Week 4 (+ 1 Week)	Week 13 (± 1 Week)	Week 26 (± 1 Week)
Target Day		Day 1	Day 29	Day 92	Day 183
Range		Day 1	Day 2 - 60	Day 61 - 137	Day 138 - EOS

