6. SUBJECT DISPOSITION

6.1. DISPOSITION

The number of subjects who are screened for the trial, the reasons for screen failure, the number of subjects who received any doses and the number of subjects who complete the trial will be presented. The frequency and percentage of subjects who withdraw or discontinue from the trial, and the reason for withdrawal or discontinuation, will also be summarized.

The summaries will be presented in a table and subject disposition data will be presented in a listing.

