8.1. ADVERSE EVENTS

AE is defined as any untoward medical occurrence in a clinical investigation subject administered a pharmaceutical product and which does not necessarily have a causal relationship with the treatment. An AE can therefore be any unfavorable and unintended sign (including abnormal laboratory finding), symptom, or disease temporally associated with the use of a medicinal (investigational) product, whether or not related to that product. An AE can arise with any use (eg, in combination with another drug), route of administration, formulation, or dose, including an overdose.

An AE is considered treatment emergent, ie, Treatment Emergent Adverse Event (TEAE), is any AE that was first occurred or worsened after the first study dose and before the end of study. If the AE has any missing start date, the rules stated in [Section 5.2](#) will be applied to determine if it is treatment-emergent.

A serious AE (SAE) is SAE is any untoward medical occurrence that:

- Results in death
- Is life-threatening
- Requires inpatient hospitalization or prolongation of an existing hospitalization
- Results in persistent or significant disability/incapacity
- Is a congenital anomaly/birth defect

Summaries of incidence rates (frequencies and percentages) of individual TEAEs by MedDRA SOC and preferred term will be prepared. Such summaries will be displayed for all TEAEs, TEAEs by maximum intensity, and TEAEs by strongest relationship to study drug. In addition, related TEAE, non-related TEAE, TEAE leading to study drug discontinuation, and serious TEAE, by SOC, the preferred term and TEAE by preferred term will be also summarized. Especially, related includes definite, probable and possible relationship. Not-related includes unlikely/remote and unrelated/not related.

Each subject will be counted only once within each preferred term. If a subject experience more than one TEAE within a preferred term, only the TEAE with the strongest relationship or the maximum intensity, as appropriate, will be included in the summaries of relationship and intensity.

Data listing of AEs, TEAE leading to study drug discontinuation, serious TEAE will also be provided.

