8.2. LOCAL TOLERABILITY

Local tolerability is defined as an injection site reaction deemed abnormal from those ordinarily observed in SC injections (including pain, intensity, or duration).

At Visit 1, assessment of local tolerability will be performed by trial staff using the Local Tolerability Scale at the time of the first study drug injection and 15 minutes, 1 hour and 2-hour post-dose. At the same time, and as part of subject diary training, the subjects/parents/legal guardians/caregivers will document their assessment of local tolerability in the subject diary, within which injection site pain will be rated by the Wong-Baker FACES Pain Rating Scale.

Between visits, local tolerability will be evaluated and documented by the subject/parent/legal guardian/caregiver in the subject diary.

At Visit 2 and Visit 3, assessment of local tolerability will be performed by injection site examination by trial staff local tolerability will be summarized based on the investigator's and subject/parents/legal guardians assessment of redness, bruising, swelling and pain.

Descriptive summary variables such as pain scale, redness, bruising and swelling will be produced for each assessment at each time point. A data listing of investigator's and subject/parents/legal guardian assessment will also be provided.

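### SAP 5.5 makes its only safety population depend on undefined follow-up data, a condition absent from Protocol 14.3, so a child dosed once who never returns could be left out of the safety tables

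*SAP*

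**What the plan says.** Protocol 14.3 has one population and one entry condition: "The analysis population includes all patients who receive at least one dose of study drug".

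SAP 5.5 defines a Screened Population and a Full Analysis Set (FAS). The FAS takes subjects with "at least one dose of study drug during the trial and who have any follow-up data". The section then states: "The efficacy and safety analysis will be performed based on Full Analysis Set". There is no separate set of all dosed subjects.

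Four other parts of the SAP bear on the point:

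- **Denominators (SAP 5).** Unless otherwise specified, "the denominator for the percentage calculation will be based upon the total number of subjects in the study population for the cohorts".
- **Disposition (SAP 6.1).** The tables report "the number of subjects who received any doses", which is a count of all dosed children.
- **Adverse events (SAP 8.1).** A treatment-emergent event is "any AE that was first occurred or worsened after the first study dose and before the end of study", so a reaction on Day 1 after the injection qualifies.
- **Local tolerability (SAP 8.2).** At Visit 1, trial staff score the injection site "at the time of the first study drug injection and 15 minutes, 1 hour and 2-hour post-dose".

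**The concern.** The SAP adds a condition that the protocol does not have, leaves its key term undefined, and applies it to safety as well as efficacy. A follow-up requirement can make sense for an efficacy set, where a child with no later height measurement contributes nothing. For safety, exposure to the drug is normally enough for entry. Once entry also depends on what happens after dosing, the denominator and the counts of treatment-emergent events depend on who comes back and on how a programmer reads the clause.

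Safety and tolerability are the sole primary objective (Protocol 6.1, SAP 2.1). What is at stake is whether a dosed child, possibly with a recorded early reaction, appears in the summary tables for that objective. The N in those tables could also differ from the dosed count in SAP 6.1, with nothing in the SAP to say which children account for the gap.

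**Working it through.** **1. The plan's own figure.** SAP 3.2 and Protocol 14.2 claim at least 95% probability of observing an event of 2% incidence with 150 subjects, and of 1% incidence with about 300. With P = 1 − (1 − p)^n:

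- 1 − 0.98^150 = 95.17%
- 1 − 0.99^300 = 95.10%

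Both claims reproduce.

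**2. What the clause could mean.** The SAP text allows two readings.

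- *Reading A: any observation after the injection counts.* The first dose is given on site and tolerability is scored for 2 hours afterwards (Protocol 10.2.2.1, SAP 8.2). Almost every dosed child would qualify, and the clause would have almost no effect.
- *Reading B: follow-up means data after Visit 1.* SAP 5.3 describes a "Post-baseline unscheduled visit (occurred after the date of initiation of the first dose" date as its post-baseline case, and the first analysis window after Visit 1 in SAP Table 2 opens on Day 2. A child with nothing recorded from Day 2 onward is then outside the FAS.

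**3. Whether the Reading B case can arise.** Children aged 3 or over have no scheduled visit between Day 1 and Visit 2, which falls on Day 82 at the earliest (SAP 5.3). Children under 3 have the Cmax Visit on Day 23 at the earliest. The diary is handed in at site visits (Protocol 9.8), so a child who never returns may leave no diary record. Loss to follow-up is a listed reason for ending participation (Protocol 7.3.1). An Early Termination Visit should be scheduled after withdrawal (Protocol 8.2), but attendance cannot be guaranteed.

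**4. Effect on a reported rate.** The documents do not say how many children would be affected. As an illustration, assume N = 150 dosed and k = 1 excluded. Let x be the number of dosed children with the event, and let e = 1 if the excluded child had it and 0 if not.

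Reported rate = (x − e) / (N − k)

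| x | All dosed | Excluded child had the event | Excluded child did not |
|---|---|---|---|
| 1 | 1/150 = 0.67% | 0/149 = 0% | 1/149 = 0.67% |
| 3 | 3/150 = 2.00% | 2/149 = 1.34% | 3/149 = 2.01% |
| 15 | 15/150 = 10.00% | 14/149 = 9.40% | 15/149 = 10.07% |

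The rate can move either way. The case that matters is the first row: a single event that disappears from the table.

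**5. Effect on detection probability.** At 2% incidence, one exclusion gives 1 − 0.98^149 = 95.07% and two give 1 − 0.98^148 = 94.97%. These changes are negligible. The planned 150 also refers to children aged 3 to 17, with those under 3 in addition (Protocol 8), so the true margin may be wider.

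**The case against.** The strongest reply is that the SAP asks for any follow-up data and does not ask for a later visit. Visit 1 tolerability scores are post-dose observations that SAP 8.2 plans to summarise, so Reading A is a natural one. On ordinary wording, a child with a recorded Day 1 reaction already has post-dose data. The visit-window rules cited for Reading B map unscheduled visits to windows; they do not decide who belongs to a population.

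Several protocol steps also make the case rare. Protocol 8.2 asks for continued observation of dosed subjects, telephone contact and an Early Termination Visit. Most injection-site reactions are not recorded as adverse events at all (Protocol 11.11.2). Nothing would be hidden either: all eCRF data are listed (SAP 5), adverse events have their own listings (SAP 8.1), and disposition shows every dosed child. The trial has a single arm, so no between-group comparison is distorted.

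Much of this stands. Reading A may be what was intended, the number affected is probably very small, and the documents do not show that children with early reactions are the ones most likely to be lost. None of it removes the conflict, however. If Reading A is intended, the clause does almost nothing and can go. If it is not, the SAP departs from the protocol on the safety population without giving a reason. Listings let a reader find an omitted child, but they do not correct the summary table.

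**Conclusion.** The concern holds. SAP 5.5 conflicts with Protocol 14.3, the added condition is undefined, and the resulting set is the only one available for the safety analysis. A child dosed once with no later data could be left out of the summary safety tables. Whether this happens depends on Reading B and on at least one such child existing; neither can be settled from the documents.

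The expected numerical effect is small. Under the assumption of one exclusion among 150 dosed, common events hardly change, but a single rare Day 1 reaction could fall from 0.67% to zero in the table. No direction of bias is claimed, and the plan's detection probabilities are not challenged. The point should be corrected because it concerns the primary objective and is easily put right.

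**What to change.** For all SAP Section 8 analyses, use every subject who received at least one dose, as Protocol 14.3 does. There are two ways to do this:

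- delete the follow-up condition from the FAS definition in SAP 5.5; or
- add a Safety Analysis Set of all dosed subjects and assign Section 8 to it. SAP 8.5, which names the FAS for the laboratory summaries, would need the same change.

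If a follow-up condition is wanted for efficacy, define it there, for example as at least one post-baseline efficacy assessment.

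The cost is one sentence in SAP 5.5 and at most one more population flag, plus the SAP 8.5 reference under the second option. A dosed child with no post-dose data would count as event-free, which lowers percentages trivially: 3/149 = 2.01% becomes 3/150 = 2.00%. The safety N would then match the dosed count in SAP 6.1.

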6. SUBJECT DISPOSITION

6.1. DISPOSITION

The number of subjects who are screened for the trial, the reasons for screen failure, the number of subjects who received any doses and the number of subjects who complete the trial will be presented. The frequency and percentage of subjects who withdraw or discontinue from the trial, and the reason for withdrawal or discontinuation, will also be summarized.

The summaries will be presented in a table and subject disposition data will be presented in a listing.

6.2. PROTOCOL DEVIATIONS

A list of major protocol deviations that could significantly affect study assessments will be identified by Clinical and the Medical Experts based on the pre-specified criteria. A data review meeting will be held to determine this list. This list will be finalized prior to database lock. A listing will be produced for major protocol deviations.

7. DEMOGRAPHICS AND OTHER CHARACTERISTICS

7.1. DEMOGRAPHICS AND DISEASE CHARACTERISTICS

Descriptive summaries of the baseline demographic and other disease characteristics will be summarized for the Full Analysis Set.

- Baseline Demographics and disease characteristics:
 - Age (years) at Visit 1
 - Age category (<3 years, ≥3 to <6 years, [≥6 to <11 years for girls, ≥ 6 to <12 years for boys] and [≥11 years for girls, ≥12 years for boys])
 - Gender
 - Race
 - Ethnicity
 - Region (North America and Oceania)
 - Absolute height (cm)
 - Height SDS
 - Weight (kg)
 - Body mass index (BMI) (kg/m²)
 - Pubertal status (Tanner stage)
 - Mother's height (cm)
 - Father's height (cm)
 - Mid-parental height SDS
 - Delta Mid-parental height SDS: subject height SDS subtract mid parental height SDS
 - IGF-1
 - IGF-1 SDS
 - IGFBP-3
 - Deficiencies of Other Pituitary Axes
 - Prior use of hGH therapy (Yes/No)
 - Current use of hGH (name, dose and duration)

- Disease Characteristics at diagnosis (prior to starting daily growth hormone therapy)
 - Age at diagnosis
 - IGF-1 SDS at diagnosis
 - IGFBP-3 SDS at diagnosis
 - Peak stimulated GH
 - Peak stimulated GH levels ≤ 5 ng/mL, >5 ng/mL
 - Bone age at diagnosis/delay in bone age
 - Results of karyotype testing
 - Other pituitary deficiencies at diagnosis

7.2. MEDICAL HISTORY

Medical history will be coded with Medical Dictionary for Regulatory Activities (MedDRA) (Version 19.0 or later). Incidences of findings in medical history will be summarized by system organ class (SOC) and preferred term.

7.3. PRIOR AND CONCOMITANT MEDICATIONS

All medications will be coded using the World Health Organization (WHO) Drug Dictionary (Version March 2016 or later). The frequency and percentage of all prior and concomitant medications will be summarized by Anatomical Therapeutic Chemical (ATC) classification and preferred term. Listings of all medications will also be provided.

For medication with missing dates, the rules stated in [Section 5.2](#) will be applied to determine if the medication is a prior or concomitant medication.

7.3.1. Prior Medication

Prior medication is defined as any medication which has a start date prior to the date of the first administration of the study drug.

7.3.2. Concomitant Medication

Concomitant medication is defined as medication taken after the first study treatment and during the trial.

Permitted Concomitant Medications

- Replacement therapy for other non-GH pituitary deficiencies.
- Glucocorticoid therapy for indications other than adrenal replacement (eg, asthma)
- Treatment for diabetes
- Over-the-counter vitamins, minerals, or other dietary supplements only if their use is agreed to by the investigator

Prohibited Concomitant Medications

- Weight-reducing drugs or appetite suppressants, unless used for management of ADHD
- hGH therapies other than TransCon hGH

Use of prohibited concomitant medications will be summarized and listed.

8. SAFETY ANALYSIS

The safety endpoints ([Section 3.3.1](#)) are measured throughout the 26 weeks of weekly TransCon hGH treatment. These safety variables will be summarized in tables and all safety evaluations will also be listed.

8.1. ADVERSE EVENTS

AE is defined as any untoward medical occurrence in a clinical investigation subject administered a pharmaceutical product and which does not necessarily have a causal relationship with the treatment. An AE can therefore be any unfavorable and unintended sign (including abnormal laboratory finding), symptom, or disease temporally associated with the use of a medicinal (investigational) product, whether or not related to that product. An AE can arise with any use (eg, in combination with another drug), route of administration, formulation, or dose, including an overdose.

An AE is considered treatment emergent, ie, Treatment Emergent Adverse Event (TEAE), is any AE that was first occurred or worsened after the first study dose and before the end of study. If the AE has any missing start date, the rules stated in [Section 5.2](#) will be applied to determine if it is treatment-emergent.

A serious AE (SAE) is SAE is any untoward medical occurrence that:

- Results in death
- Is life-threatening
- Requires inpatient hospitalization or prolongation of an existing hospitalization
- Results in persistent or significant disability/incapacity
- Is a congenital anomaly/birth defect

Summaries of incidence rates (frequencies and percentages) of individual TEAEs by MedDRA SOC and preferred term will be prepared. Such summaries will be displayed for all TEAEs, TEAEs by maximum intensity, and TEAEs by strongest relationship to study drug. In addition, related TEAE, non-related TEAE, TEAE leading to study drug discontinuation, and serious TEAE, by SOC, the preferred term and TEAE by preferred term will be also summarized. Especially, related includes definite, probable and possible relationship. Not-related includes unlikely/remote and unrelated/not related.

Each subject will be counted only once within each preferred term. If a subject experience more than one TEAE within a preferred term, only the TEAE with the strongest relationship or the maximum intensity, as appropriate, will be included in the summaries of relationship and intensity.

Data listing of AEs, TEAE leading to study drug discontinuation, serious TEAE will also be provided.

8.2. LOCAL TOLERABILITY

Local tolerability is defined as an injection site reaction deemed abnormal from those ordinarily observed in SC injections (including pain, intensity, or duration).

At Visit 1, assessment of local tolerability will be performed by trial staff using the Local Tolerability Scale at the time of the first study drug injection and 15 minutes, 1 hour and 2-hour post-dose. At the same time, and as part of subject diary training, the subjects/parents/legal guardians/caregivers will document their assessment of local tolerability in the subject diary, within which injection site pain will be rated by the Wong-Baker FACES Pain Rating Scale.

Between visits, local tolerability will be evaluated and documented by the subject/parent/legal guardian/caregiver in the subject diary.

At Visit 2 and Visit 3, assessment of local tolerability will be performed by injection site examination by trial staff local tolerability will be summarized based on the investigator's and subject/parents/legal guardians assessment of redness, bruising, swelling and pain.

Descriptive summary variables such as pain scale, redness, bruising and swelling will be produced for each assessment at each time point. A data listing of investigator's and subject/parents/legal guardian assessment will also be provided.

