10.2 Trial Periods and Visits

Following the Screening Period, enrolled subjects will attend a total of 3* morning trial visits:

- **Visit 1:** Week 1, Day 1 (1st week/day of dosing)
- **Visit 2:** Week 13 (±1 week), 5 days (±1 day) after the 12th, 13th or 14th dose
- **Visit 3:** Week 26 (±1 week), 5 days (±1 day) after the 25th, 26th or 27th dose

* All subjects < 3 years old at Visit 1, will also have the following morning visit:

- **C_{max} Visit:** Week 4 (+1 week), 1-2 days after the 4th or 5th dose

All visits should be in the morning for consistent height measurements. Attempts should be made to adhere to the planned visit schedule. It is suggested that the site staff provide dosing, diary, and visit reminders (eg, phone calls) to subjects/parents/legal guardians between visits.

An overview of all visits is provided in the Schedules of Events ([Section 18.2](#)).

For detailed descriptions of assessments refer to [Section 11](#).

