11.8 Subject Diary

The subject diary will be provided to the subject/parent/legal guardian/caregiver at Visit 1 and should be completed weekly on the day of study drug administration. The data captured within the subject diary includes:

- Date and time of administration
- Dose of study drug
- Person preparing and giving injection
- Location of injection on subject's body
- Assessment of subject pain using the Wong-Baker FACES Pain Rating Scale (see [Appendix 2](#))
- Assessment of local tolerability
- Changes to medications or subject's health

The subject diary should be reviewed by trial staff at every trial visit as part of concomitant medication review, adverse event reporting and study drug compliance.

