11.11.2 Reporting Local Tolerability as an Adverse Event

For the purpose of this trial, injection site reactions should not be documented as AEs unless the reaction:

- Impacts the subject's ability to perform daily activities, or
- Requires medical therapy (not including prophylactic therapy)

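### SAP 8.2 plans local tolerability summaries by time point only, with no 26-week count of children who had a reaction

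*SAP*

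**What the plan says.** SAP 3.3.1 lists local tolerability among the safety endpoints followed over the whole 26 weeks, and tolerability is part of the primary objective (SAP 2.1).

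The data are longitudinal. Protocol 11.8 says the diary "should be completed weekly on the day of study drug administration", and SAP 8.2 repeats that "Between visits, local tolerability will be evaluated and documented by the subject/parent/legal guardian/caregiver in the subject diary". Visit 3 falls "5 days (±1 day) after the 25th, 26th or 27th dose" (protocol 10.2), so a child who completes treatment should have 25 to 27 diary records. Trial staff rate the site around the first injection at Visit 1 and examine it at Visits 2 and 3.

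The output rule in SAP 8.2 is "Descriptive summary variables such as pain scale, redness, bruising and swelling will be produced for each assessment at each time point", followed by "A data listing of investigator's and subject/parents/legal guardian assessment will also be provided".

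Two other places bear on this:

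- Protocol 11.11.2: "For the purpose of this trial, injection site reactions should not be documented as AEs unless the reaction" interferes with daily activities or needs medical therapy.
- SAP 8.1, for treatment-emergent AEs: "Each subject will be counted only once within each preferred term". That gives a per-child incidence over the trial. SAP 8.3 likewise plans overall antibody incidences as well as by-visit summaries.

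**The concern.** A safety endpoint measured about 26 times per child is summarised one time point at a time. No specified table condenses the 26 weeks to the child: whether a reaction ever occurred, how bad the worst one was, or what share of injections caused one. For AEs and antibodies the same SAP does condense to the child.

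The AE tables cannot stand in, because protocol 11.11.2 filters injection site reactions before they reach the AE record. For every reaction that meets neither of its two conditions, SAP 8.2 is the only planned summary.

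What is at stake is how part of the primary objective reads in the report. A small percentage repeated week after week looks reassuring. It looks the same whether a handful of children react to every injection or a large share of children react at some time, and these are different tolerability profiles for a once-weekly product.

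**Working it through.** **The plan's own figure.** Protocol 14.2 and SAP 3.2 state at least 95% probability of observing an AE of 2% incidence with 150 children, and of 1% incidence with about 300.

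- 1 − (1 − 0.02)^150 = 0.9517
- 1 − (1 − 0.01)^300 = 0.9510

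Both reproduce, and this point does not change them. They concern the share of children with an event during follow-up, which is the kind of figure SAP 8.2 does not plan.

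**Which table covers which reaction**

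| Reaction | SAP 8.1 (AE tables) | SAP 8.2 |
|---|---|---|
| Interferes with daily activities or needs therapy | Child counted once per term; maximum intensity | By time point, plus listing |
| Any other | Not included | By time point, plus listing |

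**What weekly percentages determine.** Inputs: N = 150 (SAP 3.2) and k = 26 weekly injections (protocol 10.2 gives 25 to 27). The documents give no reaction rate, so p is assumed constant and shown over a range. Every child is assumed to have a record every week.

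- Minimum share ever affected (same children each week): p
- Maximum (different children each week): min(1, k × p)
- If weeks are independent: 1 − (1 − p)^k

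| Assumed p per week | Minimum | Independent | Maximum |
|---|---|---|---|
| 1% | 1% (1.5 children) | 23.0% (34.5) | 26% (39) |
| 2% | 2% (3) | 40.9% (61.3) | 52% (78) |
| 5% | 5% (7.5) | 73.6% (110.5) | 100% (150) |
| 10% | 10% (15) | 93.5% (140.3) | 100% (150) |

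At p = 2%: 150 × 0.02 = 3 children per week; 26 × 3 = 78; 1 − 0.98^26 = 0.409, and 150 × 0.409 is about 61. With k = 25 or 27 the independent value is 39.7% or 42.0%, and the maximum is 75 or 81 children.

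In every 2% scenario the share of injections with a reaction is the same: (26 × 3) / (26 × 150) = 78/3,900 = 2%. A per-injection rate could therefore be pieced together from weekly tables if each showed its number of diary entries. The per-child count cannot.

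**The case against.** The strongest reply has five parts.

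- **The data are there.** A reader might infer that the trial will be unable to say how many children ever reacted. The documents do not support that. The diary is kept weekly, SAP 8.2 lists staff and family ratings, and SAP 5 and 8 list all eCRF data and all safety evaluations. The count can be derived. What is absent is a pre-specified table. SAP 1 requires unplanned analyses to be labelled post hoc, and the choices of sign, grade, rater and handling of missing weeks would then be made in an open-label trial with the data in view. This part of the reply stands and limits the point.
- **The important reactions are counted.** Those that interfere with activities or need therapy become AEs and are counted once per child. This also stands: the gap concerns reactions below that threshold. A reader might add that most reactions fall below it, but neither document gives the share.
- **The endpoint is not worded as an incidence.** SAP 3.3.1 uses that word for AEs, antibodies and high IGF-1 SDS, but not here. By-time-point description therefore does not contradict the endpoint. It does leave a 26-week endpoint without a specified 26-week summary.
- **The text leaves room.** A run-on sentence in SAP 8.2 says in general terms that tolerability will be summarised from staff and family ratings, and the list in the quoted rule is open-ended. Neither promises a per-child result.
- **A count of any reaction may be uninformative.** Over about 26 injections, trivial redness or pain could make nearly every child positive. This is fair, and it is why the remedy should show the distribution of worst ratings. The rating scales are in appendices not visible in the public copy, so any threshold they contain could not be checked.

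**Conclusion.** The point holds as a reporting gap that should be closed, not as an error that damages the trial. SAP 8.2 specifies by-time-point summaries and a listing. It specifies no 26-week per-child count, no worst rating per child and no per-injection rate. For reactions outside the two AE conditions, no other planned table supplies them.

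On size: an assumed 2% at each of 26 injections in 150 children is compatible with 3 to 78 children ever affected, about 61 under independence. The rates are illustrative, and the maximum requires that no child reacts twice. The qualitative conclusion does not depend on the rate chosen, although the width of the range does. No hypothesis test or stated decision rule rests on this table.

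**What to change.** Keep the by-time-point tables and add to SAP 8.2, for each of redness, bruising, swelling and pain:

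1. **Per child, separately for staff and family ratings.** Number and percentage of children by worst post-dose rating on treatment, including the percentage with any rating above the lowest category of the scale used. Denominator: children with at least one post-dose assessment by that rater. State whether the staff examinations at Visits 2 and 3, which the protocol records in the limited physical examination, enter the staff rating.
2. **Per injection, from the diary.** Injections with such a rating divided by injections with a diary entry. Leave missing diary weeks out of the denominator and do not count them as no reaction. Report the number of diary entries per child, so that the per-child figure can be read against exposure.

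State the denominator for the weekly diary tables too. The SAP 5 default is the whole study population, under which a blank week could pass as no reaction.

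Cost: SAP wording and one more table per assessor, from data already collected, with no new visits or protocol change. The downside for the sponsor is presentational: on a common denominator, the per-child percentage is at least as high as any single-week figure.
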